#### **4.1.6 Packaging, labelling, and re-supply**

##### BI 894416 tablets

BI 894416 tablets will be provided by BI. They will be packaged and labelled in accordance with local law and the principles of Good Manufacturing Practice.

For details of packing and the description of the label, refer to the ISF.

The telephone number of the sponsor and the name, address and telephone number of the trial site are provided in the subject information form. The EudraCT number is indicated on the title page of this protocol as well as on the subject information and informed consent forms.

No re-supply is planned.

##### Rifampicin tablets

Rifampicin tablets will be obtained by the clinical trial site from a public pharmacy. The drug will be dispensed out of the original, unmodified packages.

#### **4.1.7 Storage conditions**

Drug supplies will be kept in their original packaging and in a secure limited access storage area in accordance with the recommended (labelled) storage conditions. If necessary, a temperature log must be maintained to make certain that the drug supplies are stored at the correct temperature. If the storage conditions are found to be outside the specified range, the clinical trial manager (as provided in the list of contacts) is to be contacted immediately.

#### **4.1.8 Drug accountability**

The investigator or designee will receive the investigational drugs delivered from the sponsor following requirements are fulfilled:

- Approval of the clinical trial protocol by the IRB / ethics committee
- Approval/notification of the regulatory authority, e.g. competent authority
- Availability of the *curriculum vitae* of the Principal Investigator
- Availability of a signed and dated clinical trial protocol

Only authorised personnel documented in the form 'Trial Staff List' may dispense medication to trial subjects. The trial medication must be administered in the manner specified in the CTP.

Proprietary confidential information © 2019 Boehringer Ingelheim International GmbH or one or more of its affiliated companies

The investigator or designee must maintain records of the product's delivery to the trial site, the inventory at the site, the use by each subject, and the disposal of unused products. These records will include dates, quantities, batch / serial numbers, expiry ('use-by') dates, and the unique code numbers assigned to the investigational medicinal product and trial subjects. The investigator or designee will maintain records that document adequately that the subjects were provided the doses specified by the CTP and reconcile all investigational medicinal products received from the sponsor. At the time of disposal of remaining trial medication, the investigator or designee must verify that no remaining supplies are in the investigator's possession.

All unused medication will be disposed of locally by the trial site upon written authorisation of the clinical trial leader. Receipt, usage and disposal of trial medication must be documented on the appropriate forms. Account must be given for any discrepancies.

## **4.2 OTHER TREATMENTS, EMERGENCY PROCEDURES, RESTRICTIONS**

### **4.2.1 Other treatments and emergency procedures**

There are no special emergency procedures to be followed. No additional treatment is planned. However, if adverse events require treatment, the investigator can authorise symptomatic therapy. In those cases, subjects will be treated as necessary and, if required, kept under supervision at the trial site or transferred to a hospital until all results of medical evaluations are acceptable.

### **4.2.2 Restrictions**

#### **4.2.2.1 Restrictions regarding concomitant treatment**

In principle, no concomitant therapy is allowed. All concomitant or rescue therapies will be recorded (including time of intake on study days) on the appropriate pages of the CRF.

Acetylsalicylic acid or other drugs that may inhibit platelet aggregation or coagulation should be avoided during the entire study.

Paracetamol, diclofenac or other drugs with relevant hepatotoxicity should be avoided during the entire study.

Known inhibitors/inducers of CYP3A and P-glycoprotein should be avoided during the entire study.

If needed, ibuprofen may be given to treat adverse events, e.g. headache.

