#### Platelet aggregation and bleeding risk

A role of SYK in platelet function has been demonstrated in literature [[R15-5470](#)]. Several platelet functions rely on SYK signalling (e.g. collagen receptor GPVI) but others are independent of SYK [[R16-5240](#)]. *In vitro* studies using human platelets demonstrated that at concentrations up to 100 µM, BI 894416 had no effect on extrinsic or intrinsic coagulation pathways. Also, BI 894416 did not inhibit ADP-induced platelet aggregation up to 100 µM. However, BI 894416 inhibited collagen- and arachidonic acid-induced platelet aggregation at 3 µM and 5 µM. However, platelet function as measured by bleeding time is not affected by a drug unless all the platelet pathways are inhibited due to redundancy within the system. Therefore, no risk for bleeding exists with regard to platelet inhibition unless a subject is also on another antiplatelet drug that blocks these other pathways. In line with this conclusion, data of previous trial 1371-0001 do not indicate any signs of an increased risk of bleeding.

*Risk mitigation and monitoring:* Use of any other concomitant drug that could reasonably inhibit platelet aggregation or coagulation (e.g. acetylsalicylic acid) will be prohibited (see Sections [3.3.3](#) and [4.2.2.1](#)). Adverse events will be monitored for any signs of bleeding or bleeding-related adverse events.

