18. Inability to comply with the dietary regimen of the trial site
19. A marked baseline prolongation of QT/QTc interval (such as QTc intervals that are repeatedly greater than 450 ms) or any other relevant ECG finding at screening
20. A history of additional risk factors for *Torsade de Pointes* (such as heart failure, hypokalaemia, or family history of Long QT Syndrome)
21. Subject is assessed as unsuitable for inclusion by the investigator, for instance, because the subject is not considered able to understand and comply with study requirements, or has a condition that would not allow safe participation in the study

In addition, the following trial-specific exclusion criteria apply:

22. History of relevant neurological disorder affecting the peripheral or central nervous system (this includes, but is not limited to: stroke, epilepsy, inflammatory or atrophic diseases affecting the nervous system, cluster headache or any cancer of the nervous system). Febrile seizures in childhood or adolescence, recovered carpal tunnel syndrome, recovered uncomplicated meningitis, recovered herpes zoster, tension headache, occasional benign tics (e.g. due to stress) or minor para- or dysesthesia (e.g. as a side effect of prior blood withdrawal) do not constitute a history of relevant neurological disorder.
23. History of immunological disease except allergy not relevant to the trial (such as mild hay fever or dust mite allergy) and except asthma in childhood or adolescence
24. History of cancer (other than successfully treated basal cell carcinoma)
25. Liver enzymes (ALT, AST, gGT, AP) above upper limit of normal at the screening examination

Proprietary confidential information © 2019 Boehringer Ingelheim International GmbH or one or more of its affiliated companies

26. Within 10 days prior to administration of trial medication, use of any drug that could reasonably inhibit platelet aggregation or coagulation (e.g., acetylsalicylic acid)
27. Male subjects with WOCBP partner who are unwilling to use male contraception (condom or sexual abstinence) from time point of first administration of trial medication until 30 days after the last administration of trial medication

For study restrictions, refer to Section [4.2.2](#).

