## **7.2 CONCOMITANT DISEASES AND MEDICATION**

Frequency tables are planned for this section of the report, based on the TS.

Concomitant diseases will be coded using the coding system of the Medical Dictionary for Drug Regulatory Activities (MedDRA). Medications will be coded using the World Health Organization Drug Dictionary (WHO-DD). The coding version number will be displayed as a footnote in the respective output.

The diagnoses and medications will be listed. Subjects without any concomitant diagnoses or concomitant therapies should be marked with a “No” in the respective column.

The relevance of the concomitant therapies to the evaluation of PK will be decided no later than at the RPM.

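### Does allowing ibuprofen in Protocol Section 4.2.2.1 undo the ban on platelet-inhibiting drugs described in Section 1.4.3.1?

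*Protocol*

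**What the plan says.** Three parts of the protocol and one of the SAP bear on this.

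- **Protocol 1.4.3.1, Platelet aggregation and bleeding risk.** It reports that in vitro "BI 894416 inhibited collagen- and arachidonic acid-induced platelet aggregation", and reasons that "no risk for bleeding exists with regard to platelet inhibition unless a subject is also on another antiplatelet drug that blocks these other pathways". The mitigation is then: "Use of any other concomitant drug that could reasonably inhibit platelet aggregation or coagulation (e.g. acetylsalicylic acid) will be prohibited". Sections 3.3.3 and 4.2.2.1 are cited for it.
- **Protocol 3.3.3, criterion 26.** Recent use of such drugs excludes a subject, over the 10 days before trial medication. Acetylsalicylic acid is the only example given.
- **Protocol 4.2.2.1.** It opens with "In principle, no concomitant therapy is allowed". It then says "Acetylsalicylic acid or other drugs that may inhibit platelet aggregation or coagulation should be avoided during the entire study", adds similar advice on hepatotoxic drugs (naming paracetamol and diclofenac) and on CYP3A and P-glycoprotein inhibitors and inducers, and ends with "If needed, ibuprofen may be given to treat adverse events, e.g. headache".
- **SAP 7.2.** Concomitant medications are coded and listed, and "The relevance of the concomitant therapies to the evaluation of PK will be decided no later than at the RPM" (the RPM is the Report Planning Meeting).

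The section on ibuprofen is the only place where either document mentions the drug.

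**The concern.** The benefit-risk argument in Section 1.4.3.1 is conditional: bleeding risk is dismissed provided the subject takes no other antiplatelet drug of a certain kind. The stated mitigation is what secures that condition. A reader who follows the cross-reference to Section 4.2.2.1 finds weaker wording and, a few lines later, permission for an anti-inflammatory drug. If ibuprofen counts as a drug that may inhibit platelet aggregation, the benefit-risk text describes to an ethics committee a safeguard that the operative section does not apply in full.

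There is also a possible consequence for the analysis. Protocol Section 7.3 lists use of restricted medication among the deviations that may lead to exclusion of a subject's pharmacokinetic data. Section 4.3 allows removal of subjects who breach trial restrictions. If the status of ibuprofen were unclear, the same dose could be classed as permitted treatment by one person and as a deviation by another. In a trial of 16 subjects, with 12 evaluable assumed for the precision calculation, each exclusion counts.

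**Working it through.** There is no planned figure to reproduce, because the point concerns wording. The check sets the sections side by side.

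**1. Strength of wording.** Section 1.4.3.1 prohibits; Section 4.2.2.1 advises avoidance. The mismatch is real. It is smaller than it looks, because the advice in 4.2.2.1 sits beneath a default under which no co-medication is allowed in principle. A platelet inhibitor is therefore disallowed in principle before the specific sentence is reached.

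**2. Is ibuprofen within the restricted class?** The documents do not say. Both restrictions name acetylsalicylic acid only as an example. Treating ibuprofen as a drug of this class is an assumption from general pharmacology. Without it, what remains is a missing link between two sentences and a difference of verb.

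**3. How Section 4.2.2.1 reads as a whole.** The order is a general default, three groups to avoid, and one named drug that may be given if needed. A specific permission placed after general restrictions in the same short section is ordinarily read as the exception. The section also steers the site away from acetylsalicylic acid, paracetamol and diclofenac, which suggests a deliberate choice, although no sentence says so. Site staff get one unambiguous instruction about ibuprofen.

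**4. Does the protocol's own condition for bleeding risk apply?** The condition is another drug acting on the pathways that BI 894416 leaves open. Section 1.4.3.1 reports no inhibition of ADP-induced aggregation up to 100 µM. Neither document says that ibuprofen blocks such a pathway. The same section reports no sign of increased bleeding in trial 1371-0001 and provides for monitoring of bleeding events.

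**5. Consequence for the analysis.** Section 4.2.2.1 requires all concomitant and rescue therapy to be recorded, with time of intake on study days. A drug that the protocol expressly permits is not, on its face, a restricted medication under Section 7.3. If a subject took it, SAP 7.2 sends the question of pharmacokinetic relevance to the Report Planning Meeting. The information and the decision point are both in place.

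**6. What a rewording would alter.**

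| Clarification | What the site does | Pharmacokinetic estimates |
|---|---|---|
| Ibuprofen labelled as an exception | as now | as now |
| Ibuprofen stated to lie outside the restriction | as now | as now |
| Same verb used in both sections | as now for ibuprofen | as now |

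Only a decision to withdraw the permission would change practice. That is a clinical decision for the sponsor's medical team, and the documents supply no ground on which a statistical review could ask for it.

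**The case for a change.** The strongest reply is that a benefit-risk section should not describe a prohibition that the section it cites does not contain, and that this holds whatever class ibuprofen belongs to. Criterion 26 does not fill the gap, because it governs entry and not the period on study. Reading ibuprofen as an intended exception does not fully rescue the text either: the permission can be read as an exception to the general default, but it is not worded as an exception to the platelet restriction, and Section 1.4.3.1 allows for none. One sentence would put it right at almost no cost.

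Much of this stands. The verbs differ, the link is missing, and a tidy protocol would have neither fault. What does not stand is the step from there to a fault in the plan. Section 1.4.3.1 is a summary that sends the reader to Section 4.2.2.1 for the rule, so anyone checking the safeguard meets the ibuprofen permission directly. The reply identifies no subject who would be handled differently, no data that would be classified differently and no estimate that would move. Low cost alone does not make a change necessary.

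**Conclusion.** The concern is right about the wording but does not support a change. Section 1.4.3.1 is worded more firmly than Section 4.2.2.1, and the ibuprofen permission is not tied to the platelet restriction. This is a drafting inconsistency that sites and analysts can resolve by reading Section 4.2.2.1 as a whole.

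Its size is nil for the primary and secondary endpoints as planned: the model, the analysis sets and the expected precision do not depend on it. The number of subjects concerned is unknown and lies between 0 and 16.

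The conclusion rests on two points. The documents do not class ibuprofen as a platelet inhibitor and show no bleeding hazard or pharmacokinetic effect from allowing it. The named permission is read as the operative instruction, with any actual use recorded and considered at the Report Planning Meeting. If the sponsor revises these sections for another reason, they should be reconciled then, with the clinical rule left to its medical team. No view is taken here on whether ibuprofen should be permitted.

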#### **4.2.2.2 Restrictions on diet and life style**

Poppy-seeds containing foods should not be consumed starting 3 days before the first drug administration in treatment period 1 until after the last PK sample in period 2 in order to avoid false-positive results in the drug screen.

Proprietary confidential information © 2019 Boehringer Ingelheim International GmbH or one or more of its affiliated companies

While admitted to the trial site, the subjects will be instructed not to consume any foods or drinks other than those provided by the staff. Standardised meals will be served at the times indicated in the [Flow Chart](#).

No food is allowed for at least 10 h before and 4 h after intake of BI 894416.

Subjects will be advised to not consume any food within at least 2 h before and 30 min after intake of rifampicin.

On Day 1 of each treatment period, from 1 h before drug intake until lunch, fluid intake is restricted to the water administered with the drug, and an additional 240 mL of water at 2 h and 4 h post-dose (mandatory for all subjects). From lunch until 24 h post-dose, total fluid intake is restricted to 3000 mL.

Grapefruits, Seville oranges (sour or bitter oranges) and their juices, and dietary supplements and products containing St. John's wort (*Hypericum perforatum*) are not permitted from 7 days before the first administration of trial medication until after the last PK sample in the second treatment period is collected.

Alcoholic beverages are not permitted from 2 days before the first administration of trial medication in period 1 until after the last PK sample in period 2 is collected.

Smoking is not allowed during the trial.

Barbecued meat and broccoli should be avoided during the trial.

Methylxanthine-containing drinks or foods (such as coffee, tea, cola, energy drinks, or chocolate) are not allowed from 10 h before until 24 h after each administration of BI 894416.

Excessive physical activity (such as competitive sport) should be avoided from 7 days before the first administration of trial medication until the end of trial examination.

Direct exposure to the sun or exposure to solarium radiation should be avoided during the entire study.

#### **4.3 TREATMENT COMPLIANCE**

Compliance will be assured by administration of all trial medication in the study centre under supervision of the investigating physician or a designee. The measured plasma concentrations of trial medication will provide additional confirmation of compliance.

Subjects who are non-compliant (for instance, who do not appear for scheduled visits or violate trial restrictions) may be removed from the trial and the CRF will be completed accordingly (for further procedures, please see Section [3.3.4.1](#)).

## 5. ASSESSMENTS

### 5.1 ASSESSMENT OF EFFICACY

Not applicable.

### 5.2 ASSESSMENT OF SAFETY

#### 5.2.1 Physical examination

At screening, the medical examination will include demographics, height and body weight, smoking and alcohol history (alcohol history not mandatory to be entered into CRF or to be reported), relevant medical history and concomitant therapy, review of inclusion and exclusion criteria, review of vital signs (BP, PR), 12-lead ECG, laboratory tests, a physical examination, and a neurological examination. At the end of trial examination, it will include review of vital signs, 12-lead ECG, laboratory tests, a physical examination, and a neurological examination.

#### 5.2.2 Vital signs

Systolic and diastolic blood pressures (BP) as well as pulse rate (PR) will be measured by a blood pressure monitor (Dinamap, ) at the times indicated in the [Flow Chart](#), after subjects have rested for at least 5 min in a supine position. All recordings should be made using the same type of blood pressure recording instrument on the same arm, if possible.

#### 5.2.3 Safety laboratory parameters

For the assessment of laboratory parameters, blood and urine samples will be collected by the trial site at the times indicated in the Flow Chart. For safety laboratory parameter sets A and B subjects should be fasted for at least 10 h. For safety laboratory parameter set C, fasting is not required. For retests, at the discretion of the investigator or designee, overnight fasting is not required.

The parameters that will be determined are listed in Tables [5.2.3: 1](#) and [5.2.3: 2](#). Reference ranges will be provided in the ISF, Section 10.

Manual differential white blood cell count or urine sediment examinations will only be performed if there is an abnormality in the automatic blood cell count or in the urinalysis, respectively.

Proprietary confidential information © 2019 Boehringer Ingelheim International GmbH or one or more of its affiliated companies

Table 5.2.3: 1

Routine laboratory tests

Functional lab group	BI test name [comment/abbreviation]	A 	B 	C 
Haematology	Haematocrit Haemoglobin Red Blood Cell Count/Erythrocytes White Blood Cells/Leucocytes Platelet Count/Thrombocytes (quant)	X X X X X	X X X X X	X X X X X
Automatic WBC differential, relative	Neutrophils/Leukocytes; Eosinophils/Leukocytes; Basophils/Leukocytes; Monocytes/Leukocytes; Lymphocytes/Leukocytes	X	X	X
Automatic WBC differential, absolute	Neutrophil, absol.; Eosinophils, absol.; Basophils, absol.; Monocytes, absol.; Lymphocytes, absol.	X	X	X
Manual differential WBC (if automatic differential WBC is abnormal and clinically relevant in the opinion of the investigator)	Neut. Poly (segs); Neut. Poly (segs), absol.; Neutrophils Bands; Neutrophils Bands, absol.; Eosinophils/Leukocytes; Eosinophils, absol.; Basophils/ Leukocytes; Basophils, absol.; Monocytes/ Leukocytes; Monocytes, absol.; Lymphocytes/Leukocytes; Lymphocytes, absol.			
Coagulation	Activated Partial Thromboplastin Time Prothrombin time – INR (International Normalization Ratio)	X X	X X	-- --
Enzymes	AST [Aspartate transaminase] /GOT, SGOT ALT [Alanine transaminase] /GPT, SGPT Alkaline Phosphatase Gamma-Glutamyl Transferase	X X X X	X X X X	X X X X
Hormones	Thyroid Stimulating Hormone	X	--	--
Substrates	Glucose (Plasma) Creatinine Bilirubin, Total Bilirubin, Direct Protein, Total C-Reactive Protein (Quant)	X X X X X X	X X X X X X	-- -- X X -- --
Electrolytes	Sodium Potassium	X X	X X	-- --
Urinalysis1 (Stix)	Urine Nitrite (qual) Urine Protein (qual) Urine Glucose (qual) Urine Ketone (qual) Urobilinogen (qual) Urine Bilirubin (qual) Urine Haemoglobin (qual) Urine WBC/Leucocytes (qual) Urine pH	X X X X X X X X X	X X X X X X X X X	-- -- -- -- -- -- -- -- --
Urine sediment (microscopic examination if haemoglobin, leukocytes nitrite or protein are abnormal in urine)	Only positive findings will be reported (for instance, the presence of sediment bacteria, casts in sediment, squamous epithelial cells, erythrocytes, leukocytes)			

 A, B, and C are different sets of laboratory values. The [Flow Chart](#) details at which time point which set is to be investigated.

The tests listed in Table [5.2.3: 2](#) are exclusionary laboratory tests that may be repeated as required. The results will not be entered in the CRF/database and will not be reported in the CTR. Except for drug screening, it is planned to perform these tests during screening only. Drug screening will be performed at screening and prior to each treatment period.

**Table 5.2.3: 2** Exclusionary laboratory tests

Functional lab group	Test name
Drug screening (urine)	Amphetamine/MDA Barbiturates Benzodiazepine Cannabis Cocaine Methadone Methamphetamines/MDMA/XTC Opiates Phencyclidine Tricyclic antidepressants
Cotinine test (urine)	Cotinine
Infectious serology (blood)	Hepatitis B surface antigen (qualitative) Hepatitis B core antibody (qualitative) Hepatitis C antibodies (qualitative) HIV-1 and HIV-2 antibody (qualitative)

To encourage compliance with alcoholic restrictions, a breath alcohol test (e.g. Alcotest® 7410, ) will be performed prior to each treatment period, and may be repeated at any time during the study at the discretion of an investigator or designee. The results will not be included in the CTR.

The laboratory tests listed in Tables [5.2.3: 1](#) and [5.2.3: 2](#) will be performed at with the exception of drug screening tests and the Cotinine test at screening. These tests will be performed at the trial site using Multidrogen Pipettier ( ), or comparable test systems.

Laboratory data will be transmitted electronically from the laboratory to the trial site.

